Screening/Enrollment. Enrollment may take place in-person at the TTRP or remotely. For details on in-person enrollment TTRP refer to protocol IRB# 6951. Remote enrollment may take place in 2 phases. In phase 1, participant eligibility will be assessed. Eligibility criteria includes: 1) annual household income of < 200% of the federal poverty guideline given household size⁴⁶, 2) > 6th grade English literacy (i.e., a 7th grade reading level is necessary to complete assessments) 3) willingness to quit smoking 7 days after enrollment, 4) ≥ 18 years of age, 5) currently smoking ≥ 5 cigarettes per day, 6) no contraindications for NRT, and 7) willingness to complete an identity check (i.e., video conference call or provide a photo ID). Participants who meet the criteria will be sent a REDCap link and will have a chance to review the consent form and HIPAA electronically. Eligible participants will be given a chance to ask questions about the research study and be asked to electronically sign both forms. Participants will also be asked to complete the baseline questionnaires and meet with their Tobacco Treatment Counselor (refer to TTRP protocol IRB# 6951 procedure). Participants will also have their smartphone assessed to determine if the INSIGHT smartphone app is compatible with their phone (currently the INSIGHT smartphone app is only compatible with Android phones). Participants who have a smartphone that is not compatible with the INSIGHT smartphone app may be mailed a study smartphone. Participants who complete phase 1 will be scheduled for a phase 2 visit and be mailed a Bedfont iCO smokerlyzer, a Greenphire clinicard, and if applicable a study smartphone. At the phase 2 appointment, the participant will be oriented to the INSIGHT smartphone app. The participant will be paid the \$30 baseline payment after completing the phase 2 appointment. Participants will have 7-10 days to complete the phase 2 appointment. Participants who do not meet the eligibility criteria or complete phase 2 in time will have the option to enroll in the TTRP for (see TTRP protocol IRB #6951) or be connected with the Oklahoma Tobacco Helpline.

Randomization. Participants will be assigned to the two treatment conditions using a form of adaptive randomization called minimization.⁴⁸ Sex (male vs. female), race/ethnicity (white vs. non-white), and CPD (≤ 10 vs. > 10) will be balanced between the treatment groups.

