Intervention Groups. Standard Care (SC). All recommended components of an intensive tobacco treatment intervention⁴⁹ will be provided. Participants will be offered an in-person counseling session to create a quit plan (during the baseline/enrollment visit), and then 5 weekly telephone counseling sessions with a Certified Tobacco Treatment Specialist. All participants will receive 12 weeks of nicotine patches, and nicotine gum or lozenges.

Contingency Management (CM). CM participants will receive SC in addition to small financial incentives for biochemically-verified abstinence. The proposed incentive amounts are similar to the schedule used in our past work^{32,33} with \$143 in possible earnings by 4 Weeks post-quit, and an additional \$105 by 6 Weeks post-quit. More specifically, CM participants may earn \$20 for quitting on the scheduled quit day (with 2 breath samples submitted and identify verification to corroborate), and may earn daily payments for quitting each day they are smoke free thereafter. Payments will start at \$3 per day and increase each week by \$1 if they remain abstinent. The daily incentive increases weekly with continued abstinence until they reach \$8 per day during week 6. Participants who smoke at any time, will not earn the incentive that day. However, they may begin earning incentives on the next full day of abstinence, though the daily incentive amount will reset to \$3 per day. Incentives may be earned daily, but they will be credited to the study credit card every Friday. (See Table 1. Compensation Schedule).

Yoking/Compensation for Samples. Participants will be asked to provide a breath sample to assess their level of smoking using the Bedfont iCO smokerlyzer from 1 week pre-quit through 12 weeks post-quit date. Participants will be asked to provide 2 breath samples per day (8 hours apart) through 6 weeks post-quit, and 1 breath sample per day through 12 weeks post-quit. Participants in the CM group will receive abstinent-contingent incentives as described above. Participants assigned to the SC group will be yoked to participants in the CM group. SC participants will receive the same payments as their CM counterparts, regardless of their abstinence status. This strategy (yoking) will be employed to equate sample submissions and payments between the groups, thereby isolating the impact of abstinence-contingent incentives on cessation.

Table 1. Compensation Schedule

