Measurement of Abstinence. Smoking abstinence will be measured via self-report and expired carbon monoxide (Bedfont iCO smokerlyzer) twice per day from the scheduled quit date through 12 weeks post-quit. Quit Day abstinence (self-report being smoke free, 2 breath samples submitted <10 and identify verification), 1 Week Post-Quit through 6 Weeks Post-Quit (self-report being smoke free, 2 breath samples submitted ≤ 6 and identify verification), and 7 Weeks Post-Quit through 12 Weeks Post-Quit (self-report being smoke free, 1 breath samples submitted ≤ 6 and identify verification).

Questionnaire Measures. We will include measures of mobile CM treatment acceptance, stress/adversity,⁵⁰⁻⁵² psychosocial resources,⁵³⁻⁵⁵ nicotine dependence/craving,^{56,57} negative affect/distress,⁵⁸⁻⁶⁰ and treatment adherence.^{61,62} Participants will complete a baseline and 12 Weeks Post-Quit assessment. Participants will be compensated for completing the \$30 for completing each assessment. Payments will be applied to participants' study credit cards. (See Table 1. Compensation Schedule). Please refer to the TTRP questionnaire appendix (IRB 6951).

Ecological Momentary Assessment. Participants will complete mobile phone-based EMAs from 1 Week pre-quit through 12 Weeks post-quit. Compensation is based on weekly completion percentages. Specifically, those who complete 50%-79% of prompted assessments will receive a \$5 credit and those who complete 80%-100% of assessments will receive a \$10 credit. EMA items were selected based on their hypothesized relations to smoking behavior, temptation and lapse episodes, and/or their potential importance in understanding the influence of socioeconomic disadvantage. Participants will self-report on smoking status and provide a breath CO sample twice per day. Participants will be prompted to complete a daily diary and 2 random assessments each day from 1-week pre-quit through 6 weeks post-quit. From 7 through 12 weeks post-quit, this will reduce to one daily diary prompt per day. Daily diaries are scheduled for each morning 30 minutes after the usual wake time. Random assessments are scheduled for twice per day during waking hours. GPS coordinates (i.e., latitude and longitude) may be collected via the smartphone during each assessment.

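### Remote enrollees need no biochemical proof of smoking at entry, so for anyone already at or below 6 ppm CO the verified abstinence outcome reduces to self-report

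*Protocol*

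**What the plan says.** The same seven eligibility criteria appear three times in the Protocol: under Eligibility Criteria and Screening/Enrollment (both B.III) and in section D, Protection of Human Subjects. The smoking criterion is a cigarettes-per-day threshold with no CO or cotinine floor: "5) currently smoking ≥ 5 cigarettes per day, 6) no contraindications for NRT, and 7) willingness to complete an identity check".

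For remote enrollment the order of events is stated. "In phase 1, participant eligibility will be assessed". Then: "Participants who complete phase 1 will be scheduled for a phase 2 visit and be mailed a Bedfont iCO smokerlyzer". The study procedure described for that visit is app training: "At the phase 2 appointment, the participant will be oriented to the INSIGHT smartphone app". In-person enrollment is handled elsewhere: "For details on in-person enrollment TTRP refer to protocol IRB# 6951".

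Measurement of Abstinence requires a smoke-free self-report and identity verification plus a CO limit. The limit is below 10 on the quit day. For weeks 1 to 6 it reads "2 breath samples submitted ≤ 6 and identify verification". For weeks 7 to 12 a single sample at or below 6 suffices. The primary outcome is biochemically verified 7-day point prevalence abstinence at week 12.

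Pre-quit samples are also taken, under Yoking/Compensation for Samples, "to assess their level of smoking using the Bedfont iCO smokerlyzer from 1 week pre-quit through 12 weeks post-quit date". No entry rule in the Protocol uses them.

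**The concern.** A CO cut-off verifies abstinence only in someone whose CO would be above it when smoking. The Protocol never establishes this for a remote enrollee. The identity check in criterion 7 shows who the person is, not that the person smokes.

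Two kinds of enrollee are affected: people who smoke little or not at all, and low-CO smokers who later report abstinence wrongly. For both, the CO component of the outcome carries no information. Recruitment is partly through social media, enrollment can be fully remote, and the automation is meant to remove close staff oversight, so nothing else in the described process would detect them.

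At stake is the trial's main product. Sample Size/Analysis Plan says the 40 participants are there to supply effect size estimates for a full-scale trial. Enrollees who count as abstinent whatever their arm raise both rates and shrink the apparent effect.

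**Working it through.** **The plan's own figure.** The Protocol states no power calculation to reproduce. Its one relevant total is the maximum abstinence-contingent payment (Table 1):
- Week 1: 20 + 6×3 = 38.
- Weeks 2 to 6: 7×4, 7×5, 7×6, 7×7, 7×8 = 28, 35, 42, 49, 56.
- By week 4: 38 + 28 + 35 + 42 = 143. Weeks 5 and 6: 49 + 56 = 105. Total: $248, as stated.

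A CM participant at or below 6 ppm throughout who reports being smoke free could collect all of it. Table 1 shows no such payment in weeks 7 to 12.

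**Logic of the outcome rule.** If CO at entry is 6 or less and stays there, the quit-day limit (below 10) and the later limit (6 or less) are both met. Identity verification is met by the right person blowing. Only the self-report remains to decide the outcome.

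**Size, as an illustration.** Inputs:
- True 12-week rates p: 20.3% (CM) and 7.8% (usual care), from Preliminary Studies, PREVAIL Pilot. These are continuous abstinence, not this trial's point prevalence.
- Share f of such enrollees, equal in both arms: not in the documents. Assumed 10%, shown from 5% to 20%.
- All of them report abstinence: assumed.
- Two-sided 5% level, 80% power, 1:1 allocation: assumed for the later trial.

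Observed rate: p′ = p + f(1 − p). At f = 10%:
- CM: 0.203 + 0.10×0.797 = 0.2827.
- SC: 0.078 + 0.10×0.922 = 0.1702.
- Risk difference: 0.2827 − 0.1702 = 0.1125, which is 0.125×(1 − 0.10).
- Odds ratio: (0.2827/0.7173) / (0.1702/0.8298) = 1.92.

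The n per arm uses the two-proportion formula with pooled variance under the null:
n = [1.96√(2p̄(1−p̄)) + 0.8416√(p₁(1−p₁) + p₀(1−p₀))]² / (p₁−p₀)², rounded up.

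| f | CM | SC | Risk difference (points) | Odds ratio | n per arm |
|---|---|---|---|---|---|
| 0 | 20.3% | 7.8% | 12.5 | 3.01 | 121 |
| 5% | 24.3% | 12.4% | 11.9 | 2.26 | 166 |
| 10% | 28.3% | 17.0% | 11.3 | 1.92 | 217 |
| 20% | 36.2% | 26.2% | 10.0 | 1.60 | 337 |

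**In this trial.** With 20 per arm, one such participant is 1/20 = 5 points of an arm's rate. If two are among the 40, simple 20/20 allocation puts both in one arm with probability 2×(20×19)/(40×39) = 0.49, a 10-point shift in that arm. Minimization balances sex, race/ethnicity and cigarettes per day, but not CO.

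**The case against.** **The magnitude is assumed.** Nothing in the documents says how many treatment-seekers reporting at least 5 cigarettes a day would read 6 ppm or less, or that all would report abstinence at week 12. Even at 10% the risk difference moves by only 1.25 points, while its standard error at 20 per arm is about 11 points: √[(0.203×0.797 + 0.078×0.922)/20] = 0.108. The Resource Sharing Plan itself says the data will not support conclusions. All of this stands. The figures show direction and scale and are not estimates.

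**A reader might infer a systematic bias toward CM**, because a claim of abstinence earns money in CM, whereas SC payments are yoked and do not depend on the participant's own status. The documents do not support that for the primary outcome. Contingent payments stop after week 6 and the outcome is at week 12, when claiming abstinence pays nothing in either arm. Carry-over of false reporting would be speculation. What can be expected is dilution, plus chance imbalance.

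**A reader might extend the point to all participants, or read the $570 total as a motive for fraud.** Neither is supported. In-person enrollment follows IRB# 6951, which is not shown, and General Procedures mentions CO collection at the clinic. Remote enrollees also meet a counselor under that protocol, though the text places this before the monitor is mailed. Of the $570, only $248 depends on abstinence (in SC, on the yoked partner's abstinence). The rest pays for questionnaires, phone assessments and samples.

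**Analysis of pre-quit CO may be in a SAP.** A baseline CO summary or sensitivity analysis is ordinary SAP content, so its absence is no fault here. The point rests on the entry criteria, which belong in the Protocol.

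**Conclusion.** The point holds for the remote route. Entry rests on reported smoking alone, and a participant already at or below 6 ppm satisfies every CO threshold unchanged, so the primary outcome is not biochemically verified for that person. The expected effect is higher abstinence in both arms and a diluted contrast.

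Under the stated assumptions (10% of enrollees, all reporting abstinence, pilot continuous-abstinence rates), the risk difference falls from 12.5 to 11.3 points and the odds ratio from 3.0 to 1.9. The n per arm for a later trial rises from 121 to 217. The true share is unknown.

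This is a weakness in design that is cheap to close. The Protocol does not contradict itself here, and no claim of bias in favor of CM at week 12 follows.

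**What to change.** At the phase 2 appointment, or at the in-person baseline, take one identity-verified iCO reading before randomization. Randomize only if it exceeds 6 ppm, the trial's own abstinence cut-off, and allow one repeat on another day. Add this as a line to the eligibility criteria in all three places where they are listed.

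The device and the appointment already exist. The cost is that a few genuine light smokers with low CO are not randomized. That matters somewhat, because the trial admits people from 5 cigarettes a day and balances a stratum of 10 or fewer.

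If no entry cut-off is wanted, report CO by arm and repeat the primary comparison without participants at or below 6 ppm. Use only readings taken before randomization. The Protocol does not say whether randomization precedes the pre-quit week. Excluding people on later readings could remove CM participants who cut down early, and so introduce a bias of its own. This alternative costs a few lines of analysis.
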